**Secondary endpoints:**

- Safety assessments will consist of monitoring and recording adverse events, including serious adverse events. Safety will be assessed by the National Cancer Institute's (NCI) Common Toxicity Criteria for Adverse Events (CTCAE), version 3.0 ([//ctep.cancer.gov/protocolDevelopment/electronic\\_applications/docs/ctcae3.pdf](http://ctep.cancer.gov/protocolDevelopment/electronic_applications/docs/ctcae3.pdf)).
- Age at Tanner Stage II-V
- Age at start of menses (menarche) – for females
- Age at thelarche – for females
- Age at adrenarche – for males
- TAND Checklist - individual responses over time since the enrollment date
- Indirect comparison between CRAD001M2305 and CRAD001MIC03 will be performed on the following endpoints:
  - Percentage of patients who achieved Tanner Stage V at or before age of 16 (females) or 17 (males).
  - Height/BMI standard deviation score by year since baseline

Objectives and related endpoints are described in [Table 3-1](#) below.

**Table 3-1 Objectives and related endpoints**

Objective	Endpoint	Analysis
Primary objective:		
Monitoring growth and development of pediatric patients with TSC-associated SEGA who are taking everolimus or have taken everolimus by annual measurements of height, weight for BMI, and Tanner Stage	Percentage of patients who achieved Tanner Stage V at or before age of 16 (females) or 17 (males). Height/BMI standard deviation score by year since baseline Mean endocrine laboratory values (FSH, LH, and estrogen or testosterone) by age	Refer to Section 10.4 .
Secondary objectives:		
Determine timing of developmental milestones: menarche (females), thelarche (females), adrenarche (males), Tanner Stage II-V Assess neuropsychological development	Age at start of menses (menarche) – for females Age at onset of breast development (thelarche) – for females Age at pubic hair development (adrenarche) – for males Age at Tanner Stage II-V - all patients TAND Checklist individual responses over time since the enrollment date	Refer to Section 10.5.1 .
Compare CRAD001M2305 and CRAD001MIC03 on height, BMI and sexual development (using Tanner Stages)	Indirect comparison between CRAD001M2305 and CRAD001MIC03 will be performed on the following endpoints: Percentage of patients who achieved Tanner Stage V at or before age of 16 (females) or 17 (males). Height/BMI standard deviation score by year since baseline.	
Safety as assessed by the NCI Common Toxicity Criteria, version 3.0.	Safety will be assessed by the National Cancer Institute’s (NCI) Common Toxicity Criteria for Adverse Events (CTCAE), version 3.0 ( //ctep.cancer.gov/protocolDevelopment/electronic_applications/docs/ctcae3.pdf ). Notes: 
 
• Safety assessments will consist of monitoring and recording adverse and serious adverse events
 
• Safety follow-up as per product information
 
	

## 4 Study design

### 4.1 Description of study design

This is a prospective, multi-center, long-term follow-up, Post-Authorization Safety Study (PASS) evaluating the growth and development of pediatric patients who are currently being treated with everolimus or who have previously been treated with everolimus for TSC-associated SEGA in [CRAD001M2301]. The study will include all consenting pediatric patients who at the time of completion of study CRAD001M2301 have not achieved Tanner Stage V and are younger than 16 years (for females) or 17 years (for males), and were receiving treatment with everolimus in study [CRAD001M2301] within 6 months before enrollment into CRAD001M2305.

According to [CRAD001M2301] enrollment figures, it is anticipated that at the time of the start of study CRAD001M2305, approximately 50 patients may be eligible for this study, if they consent to participate.

#### Enrollment

Enrollment into CRAD001M2305 will start at the conclusion of the parent protocol ([CRAD001M2301]). Investigators will identify study patients who qualify for enrollment into CRAD001M2305 and assign each a unique patient number (refer to Section 6.3).

All pediatric patients and his/her parents or legal guardian must be thoroughly informed about the study. The Informed Consent Form(s) for CRAD001M2305 must be signed prior to performing any study procedures.

Once Informed Consent has been obtained and eligibility is confirmed (Tanner Stage and age have been verified) by the investigator, the patient may be enrolled in the study.

#### Monitoring

For patients taking everolimus, dosing should follow the local product information.

Patient visits will occur every 3 months ( $\pm$  14 days) for collection of adverse events, any Afinitor/Votubia-related SAEs, and date of menarche (females). This information will be obtained from the patient or their parents/caregiver, depending on the patient's age and cognitive abilities.

Visits will also occur annually ( $\pm$  30 days) for measurement of growth (height, weight), development (Tanner staging, age at thelarche, age at menarche for females, age at adrenarche for males), and pregnancy testing. Height and weight should be measured with the same calibrated equipment and in the same manner, preferably with the patient wearing minimal clothing and no shoes at every respective visit. If possible these measurements should be obtained by the same site personnel throughout the study.

A blood sample will be taken at the annual visits for assessment of hormone levels at a local laboratory, starting at age 10 until study participation is ended. Estrogen, luteinizing hormone,

and follicular stimulating hormone will be tested for females and testosterone, luteinizing hormone, and follicular stimulating hormone for males.

Adverse events should be collected, by the investigator, according to the protocol requirements. Afinitor/Votubia-related SAEs should be collected throughout the study until 30 days after last everolimus dose.

Additionally, medications and therapies/non-drug therapies should be recorded on the CRFs designated to record concomitant medications at every 3-month and annual visit until the end of the study.

The date of the first dose and the date of the last dose of systemic everolimus treatment will be recorded, as available. The patient's recent everolimus Cmin (i.e. obtained since the last visit as per local product information) with collection date and current prescribed everolimus dose should be recorded. The time-normalized Cmin value will be estimated for the entire treatment period using recorded everolimus Cmin values and prescribed doses in that treatment period ([Section 10.5.2](#)). Additionally, a summary of everolimus interruptions (an estimate of the duration of the interruptions) will be collected at each study visit.

[figure not shown]
The dates of all performed brain MRI scans that are done in the scope of the regular TSC SEGA follow-up will be collected at the annual visits. Brain MRI data will not be collected at this point but may be retrieved at a later date if technological advancements pertaining to predicting future cognitive abilities such as the development of the working memory arise.

Brain development will be assessed by determining the occurrence of TSC-Associated-Neuropsychiatric-Disorders (TAND) with an appropriate TAND Checklist at each annual visit.

The first study visit will occur 3 months after enrollment in CRAD001M2305 and the first annual visit one year ( $\pm 30$  days) after enrollment in CRAD001M2305. The 3-monthly visits can be performed per telephone unless a visit to the site is clinically indicated.

Patient participation in the study will be completed once the patient has achieved Tanner Stage V or age 16 for females, age 17 for males, whichever occurs first.

**Figure 4-1 Study flowchart**

## 4.2 Timing of interim analyses and design adaptations

No formal interim analysis is planned for this study. However, safety outputs may be generated for regulatory safety updates.

## 4.3 Definition of end of the study

The study will end when all patients have either reached Tanner Stage V, or age 16 for females, age 17 for males, or when the last patient is discontinued. The latest possible LPLV date is expected to take place in September-2026.

## 4.4 Early study termination

The study can be terminated at any time for any reason by Novartis. The investigator may be informed of procedures to be followed in order to ensure that adequate consideration is given to the protection of the patient's interests. The investigator will be responsible for informing IRBs and/or ECs of the early termination of the trial.

# 5 Population

## 5.1 Patient population

The target population is comprised of pediatric female and male patients who have previously participated in the study [CRAD001M2301] and have not, prior to enrollment into CRAD001M2305, reached age 16 for females, or age 17 for males. Additionally, these patients will not yet have achieved Tanner Stage V. Study treatment in study [CRAD001M2301] must have been completed within 6 months prior to enrollment into CRAD001M2305.

The investigator or designee must ensure that only patients who meet all inclusion are offered participation in the study. No additional exclusions can be applied by the investigator, in order that the study population will be representative of all eligible patients. All screening assessments must be completed and reviewed by the investigator (or designee) prior to starting study participation in CRAD001M2305.

All pediatric study patients and their parent(s) or legal guardian must be thoroughly informed about all aspects of the study, including the study visit schedule and required evaluations, and all regulatory requirements in order to ensure informed consent. The written informed consent must be obtained prior to performing any CRAD001M2305 study procedures. If the patient is unable to read, an impartial witness and/or the patient's parent or legal guardian must be present during the entire informed consent discussion. The following criteria apply to all patients enrolled into the study.

## 5.2 Inclusion criteria

Patients eligible for inclusion in this study have to meet **all** of the following criteria:

1. Pediatric female patients who were on study treatment in study [CRAD001M2301] within the past 6 months and have not reached Tanner Stage V or age 16 at the time of

completion of [CRAD001M2301]  
or

2. Pediatric male patients who were on study treatment in study [CRAD001M2301] within the past 6 months and have not reached Tanner Stage V or age 17 at the time of completion of [CRAD001M2301].
3. Written informed consent according to local guidelines.

Tanner Staging results that were obtained and documented within 6 months prior to enrollment into CRAD001M2305 may be used for enrollment decisions.

### 5.3 Exclusion criteria

1. Pediatric female patients who were on study treatment in CRAD001M2301 and have not reached Tanner Stage V but are within 3 month of turning age 16  
or
2. Pediatric male patients who were on study treatment in CRAD001M2301 and have not reached Tanner Stage V but are within 3 months of turning age 17
3. Any patient who was pregnant prior to start of CRAD001M2305

## 6 Treatment

This study does not require treatment with any medication.

### 6.1 Monitoring everolimus dosing

At the discretion of the investigator, patients may be treated with commercially available everolimus, as per local product information / standard of care. Dosing will be based on locally performed PK analyses. Novartis will not perform any PK analyses. Treatment duration and dose modifications will be at the investigator's discretion, as per the local product information.

**Table 6-1 Dose and treatment schedule (if continuing on everolimus)**

Everolimus treatments	Pharmaceutical form and route of administration	Dose	Frequency and/or Regimen
Commercially available everolimus	Tablet for oral use or dispersible tablet for oral use	As per local product information/ investigator discretion	As per local product information / investigator discretion

### 6.2 Concomitant medications

Concomitant medications should be collected, by the investigator, according to the protocol requirements.

## **6.3 Patient numbering, everolimus exposure**

### **6.3.1 Patient numbering**

Each patient is identified in the study by a Patient Number (Patient No.), that is assigned when the patient is first enrolled and is retained as the primary identifier for the patient throughout his/her entire participation in the trial. The Patient No. consists of the Center Number (Center No.) (as assigned by Novartis to the investigative site) with a sequential patient number suffixed to it, so that each subject is numbered uniquely across the entire database. Upon signing the informed consent form, the patient is assigned to the next sequential Patient No. available.

### **6.3.2 Everolimus exposure**

For patients being prescribed Afinitor/Votubia, the sponsor will monitor the exposure by requesting that the investigator record in the CRF the current prescribed dose, a summary of everolimus interruptions, and any available everolimus trough concentration levels (completed as per label) that have been recorded in the patient chart. This information must also be recorded in the source document at each patient visit.

## **7 Visit schedule and assessments**

### **7.1 Study flow and visit schedule**

[Table 7-1](#) lists all of the assessments and indicates with an “X”, the visits when they are performed. All data obtained from these assessments must be supported in the patient’s source documentation.

No CRF will be used as a source document.

	Day 1 / Enrollment	Every 3 months after Day 1 (3-monthly visits that coincide with the annual visits are skipped (every 4 th 3-monthly visit))			First annual visit	Every 3 months after each consecutive year (3-monthly visits that coincide with the annual visits are skipped (every 4 th 3-monthly visit))	Annually after first year	Study completion
Time Point (months)	0	3	6	9	12	15, 18, 21, 27...	24, 36...	Last
Visit No.	1	2	3	4	5	6, 7, 8, 10...	9, 13...	778
Visit Window		± 14 days			± 30 days	± 14 days	± 30 days	
Any available everolimus blood trough levels (C min ) as per label (D) (only while on everolimus treatment)	X	X	X	X	X	X	X	X
Prescribed everolimus dose (D) (only while on everolimus treatment)	X	X	X	X	X	X	X	X
Summary of dose interruptions (D) (only while on everolimus treatment)	X	X	X	X	X	X	X	X
Brain MRI scan dates (as available) (D)					X		X	
TAND Checklist (D)	X				X		X	
End of everolimus treatment (D)		X (as applicable, complete follow-up for safety 30-days after last dose)						

### **7.1.1 Eligibility enrollment**

Patients have to be thoroughly informed about the study by the investigator and have to sign the informed consent form before study enrollment can be performed. The inclusion/exclusion criteria should be verified within 28 days before Day 1. If Tanner Staging was done in the scope of [CRAD001M2301] within 3 months prior to enrollment into CRAD001M2305, these results may be used for enrollment decisions. In this case, Tanner Staging does not have to be repeated. The patient's age should be verified prior to enrollment into CRAD001M2305.

#### **7.1.1.1 Patient demographics and other characteristics at study start**

At time of enrollment, patients' demographic and previous study identification from the parent protocol (CRAD001M2301) will be collected. Furthermore patients will undergo Tanner Staging, height, weight, and developmental milestone (adrenarche, thelarche, menarche) assessments.

Data pertaining to ongoing adverse events and concomitant medications will be transferred from the parent study into CRAD001M2305.

For details of assessments, refer to [Table 7-1](#).

### **7.1.2 Study participation**

At the discretion of the investigator, patients may continue treatment of their TSC-associated SEGAs with commercially-supplied everolimus. Everolimus does not need to be actively in use for the entire duration of the patient's study participation.

### **7.1.3 Study completion**

Patients will meet the criteria for study completion upon demonstrating Tanner Stage V, or reaching age 16 (females) or age 17 (males), whichever comes first. Upon meeting the criteria for study completion, the patient should schedule an End of Study visit at the site. The End of Study visit cannot be completed via telephone contact.

Patients who discontinue commercial everolimus should continue study participation until meeting any of the aforementioned criteria for study completion. The discontinuation of everolimus will be recorded on the End of Treatment CRF page. Safety monitoring should be continued for at least 30 days following the last dose of everolimus.

Patients who complete the study, or discontinue the study early, should have the reason for exiting the study recorded on the Study Phase Completion Disposition CRF (SEC) page.

#### **7.1.3.1 Criteria for early study discontinuation**

Patients may voluntarily withdraw from the study or be dropped from it at the discretion of the investigator at any time. Patients must be withdrawn from the study if any of the following occur:

- Protocol deviation(s) that impact eligibility
- Patient withdrew consent
- Lost to follow-up

- Administrative problems
- Death

#### **7.1.4 Post-study follow up period**

All patients must have safety evaluations 30 days after the last dose of everolimus.

Patients lost to follow up should be recorded as such on the CRF. For patients who are lost to follow-up, the investigator should show "due diligence" by documenting in the source documents steps taken to contact the patient, e.g., dates of telephone calls, registered letters, etc.

### **7.2 Assessment types**

#### **7.2.1 Efficacy assessments**

Not applicable

#### **7.2.2 Safety and tolerability assessments**

Safety will be monitored by collecting data about growth, development, and adverse events. For details on AE collection and reporting, refer to [Section 8.1](#).

##### **7.2.2.1 Height and weight**

Height and body weight (with minimal clothing, without shoes) will be measured annually. Note: CRFs are designed to collect the data in the units they are measured in; e.g., height in centimeters (cm) or inches (in) and weight in kilograms (kg) or pounds (lb). Height and weight should be measured with the same calibrated equipment and in the same manner at every respective visit. If possible these measurements should be obtained by the same site personnel throughout the study.

##### **7.2.2.2 Tanner staging**

For all male patients, Tanner Stage V will be achieved once the patient has demonstrated either stage 5 genitalia development or stage 5 pubic hair development. For all female patients, Tanner Stage V will be achieved once the patient has demonstrated either stage 5 breast development or stage 5 pubic hair development ([Marshal 1969](#), [Marshal 1970](#)).

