## Development

In animal studies it was shown that signaling through mTOR was at least partially involved in the control of puberty onset. Chronic blockade of mTOR by rapamycin had a strong inhibitory impact on puberty onset in female rats. Preliminary results suggested that also male rat puberty is sensitive to mTOR inactivation. Toxicology studies performed with everolimus demonstrate that treatment with everolimus may be associated with decreased weight in rodent pups and a delay in descent of testes in male pups.

Additionally, the safety profile of everolimus in Study [CRAD001M2301] was consistent with that observed in the phase II study [CRAD001C2485] in patients with TSC with the exception of three cases of secondary amenorrhea. Secondary amenorrhea is thought to be an indicator of end-stage ovarian dysfunction. It has been speculated that this finding may be a consequence of TSC-related-mTOR over-expression or mTOR inhibition.

Due to these preclinical and clinical findings further investigation of possible effects of long-term everolimus treatment on the onset of puberty and development of TSC patients is imperative. This study is designed to address these questions. The timing of puberty onset and development through the different stages to full maturation will be monitored by assessment of Tanner Stage and if achieved prior to study completion timing of menarche and thelarche (females) or adrenarche (males).

In addition, many of the patients who will be enrolled in this study have previously received and will be taking antiepileptic drugs (or enzyme-inducing antiepileptic drugs [EIAED]). While in general it is not thought that antiepileptic drugs impact ultimate height, the studies have not been comprehensive (Macardle et al 1986). Additionally, some antiepileptic drugs (e.g., valproic acid, topiramate) may affect weight in the peri-pubertal period (Novak et al 1999). As a consequence, this study may generate some observations about the dual exposure of patients to antiepileptic drugs and everolimus.

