#### **Primary endpoints:**

Growth and development of pediatric patients with TSC-associated SEGA who are taking everolimus or have previously taken everolimus will be monitored via:

- Percentage of patients who achieved Tanner Stage V by age 16 (for females) or age 17 (for males)
- Height, standard deviation score by year since baseline

- BMI, standard deviation score by year since baseline
- Mean endocrine laboratory values (FSH, LH, and estrogen or testosterone) by age

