3.8.2 Tanner Stage

For CRAD001M2305 patients, all data described below will be pooled with the corresponding data from Study CRAD001M2301.

Tanner Stage will include two components for boys (testis and pubic hair) and two components for girls (breast development and pubic hair).

Percentage of patients who will have reached Tanner Stage V by age 16 (for females) or age 17 (for males) will be provided, side by side, on the FAS Puberty of the studies CRAD001M2305 and TOSCA, along with 95% confidence intervals.

If the number of CRAD001M2305 patients is sufficient and notably high abnormality, the relationship between the everolimus exposure and the Tanner Stage will be further explored as detailed below:

- The percentage of patients who will have reached Tanner Stage V by age 16 (for females) or age 17 (for males) will be described in the different subgroups defined by duration of everolimus exposure. These subgroups are described in the Section 3.12.
- The duration of exposure and the age at start of everolimus will be summarized using descriptive statistics in the subgroups of patients who will reach and who will not reach Tanner Stage V by age 16 (for females) or age 17 (for males).
- A logistic regression including the duration of exposure and the age at the start of everolimus as continuous covariates may also be used to further explore if needed the relationship between the everolimus exposure and the achievement of Tanner Stage V by age 16 (for females) or age 17 (for males). Additional covariates (e.g. time normalized C_{min}) might also be included in the model.

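### Either component alone satisfies Tanner Stage V and ends follow-up, so a delay confined to breast or genital development is diluted in the primary Stage V percentage and in age at Stage V; results by component should be added.

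*Protocol*

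**What the plan says.** **Definition.** Protocol 7.2.2.2 treats Stage V as reached in boys once the patient "has demonstrated either stage 5 genitalia development or stage 5 pubic hair development". For girls the condition is having "demonstrated either stage 5 breast development or stage 5 pubic hair development". This section defines Stage V only; neither document says how the two components combine for Stages II to IV.

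**Use.** The percentage at Stage V by age 16 (females) or 17 (males) is a primary endpoint (Protocol Section 3, 10.4.1.3; SAP 2.4.2, 3.8.2). Age at each of Stages II to V is secondary and is summarised by Kaplan-Meier (Protocol 10.5.1.3; SAP 3.9.2).

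**Exit.** Protocol 4.1 says "Patient participation in the study will be completed once the patient has achieved Tanner Stage V" or the age limit, whichever comes first; Protocol 7.1.3 repeats the rule.

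**SAP.** Section 3.8.2 says "Tanner Stage will include two components for boys (testis and pubic hair) and two components for girls", but gives no combination rule and plans no percentage or age by component.

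**The concern.** A boy with pubic hair at stage 5 and genitalia at stage 3 counts as fully mature in the primary puberty endpoint and leaves the study, so his later genital course is not observed. The same applies to a girl whose breast development lags.

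The composite takes the earlier of two ages, so it is least sensitive when only one component is slowed. The study's motivation leans towards gonadal effects: Protocol 1.1.3 cites inhibited puberty onset in rats, "a delay in descent of testes in male pups", and cases of secondary amenorrhea. If everolimus slowed breast or genital development and spared pubic hair, the Stage V percentage would err in the reassuring direction.

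**Working it through.** **1. Direction.** This needs no assumption about rates. Write G for breast/genital stage 5 by the age limit and H for pubic hair stage 5 by then.

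P(either) = P(G) + P(H and not G) ≥ P(G).

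The reported percentage equals or exceeds breast/genital completion, and the composite age equals or precedes the breast/genital age.

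**2. Document figures.** The documents give no expected rate, power or component age for Stage V, so there is no stated figure to reproduce. The interval method can be checked. SAP 2.4.2.2 specifies exact Clopper-Pearson limits, and SAP 4.2 tabulates them for 15 patients. Recomputed, 9/15 gives 32% to 84% and 13/15 gives 60% to 98%, as tabulated.

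**3. Size of the dilution in mean age (illustration).** Assumptions, none from the documents: the two ages at stage 5 are bivariate normal with SD 1 year and correlation ρ of 0.5 or 0.8, and a 1-year delay affects breast/genitalia only. Let δ be the breast/genital mean minus the pubic hair mean before the delay, and s = √(2(1−ρ)), which is 1.000 or 0.632. Then

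E[earlier age] = (pubic hair mean) − L(δ), where L(δ) = s·φ(δ/s) − δ·Φ(−δ/s).

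The delay raises δ by 1, so the composite shifts by L(δ) − L(δ+1) years.

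| Pubic hair relative to breast/genital | ρ = 0.5 | ρ = 0.8 |
|---|---|---|
| 1 year earlier (δ = 1) | 0.0833 − 0.0085 = 0.07 | 0.0154 − 0.0001 = 0.02 |
| equal means (δ = 0) | 0.399 − 0.083 = 0.32 | 0.252 − 0.015 = 0.24 |
| 1 year later (δ = −1) | 1.083 − 0.399 = 0.68 | 1.015 − 0.252 = 0.76 |

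**4. The same model as a percentage.** Put the breast/genital mean at 15 years and the limit at 16, the girls' limit. A 1-year delay lowers breast/genital stage 5 by 16 from Φ(1) = 84% to Φ(0) = 50%. The either-component percentage is 1 − P(both ages above 16):

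- equal means: 94% to 87% (ρ = 0.5), 90% to 85% (ρ = 0.8);
- pubic hair 1 year later: 87% to 67% (ρ = 0.5), 85% to 60% (ρ = 0.8).

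With 15 patients, one patient is 1/15 = 6.7 points, so a fall from 94% to 87% is about one patient.

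**5. What the actual sample could look like (hypothetical counts).** Suppose 13 of 15 meet the either-component rule, nine of them with breast/genital stage 5 and four who left on pubic hair alone before the age limit. The either-component result is 13/15 = 87% (60% to 98%). The breast/genital result is 9/15 = 60% (32% to 84%) if the four are counted as not reached, and 13/15 if counted as reached.

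**6. Other outputs that could show the delay.**

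- Hormone values by age are themselves a primary endpoint (Protocol Section 3), with individual graphs and listings (SAP 3.8.3).
- Thelarche and menarche are secondary endpoints in girls.
- Potential delayed puberty (SAP 3.9.2) names both components at Stage II, and menarche in girls. Its wording can mean failure in both components or failure to attain both; under the first reading pubic hair can again mask a lag. For boys it ends at Stage II by age 14.
- Study collection of all of these stops at exit. A girl who leaves on pubic hair before 15 is not observed for menarche by 15.

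**The case against.** The either-component rule is explicit and referenced, so it is a design choice and not an error. No passage says that pubic hair stage 5 is independent of the gonads; Table 3-1 uses the term adrenarche for male pubic hair only. The motivating signals also map poorly to Stage V: puberty onset corresponds to Stage II, and testicular descent and amenorrhea are not Tanner components. No test of percentage rates is planned (SAP 2.4.2.1), and with 15 patients the records can be read individually. All of this stands and limits the weight of the point. It does not remove the bias in the two Stage V outputs, and component-level listing is not stated.

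A reader might infer four stronger things that the documents do not support:

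- *The delay is hidden from the study.* The outputs in step 6 of the working contradict this.
- *The composite can never move by more than 0.25 to 0.40 year.* That ceiling, L(0), holds only for equal component means. If pubic hair averages 1 year later it is L(−1), above 1 year.
- *Boys have no milestone other than pubic hair.* Age at Stages II to V covers all patients, and the boys' delayed-puberty rule names the testis.
- *The breast/genital component should become primary, or the completion rule should change.* Both are debatable redesigns, and the first would displace a pre-specified endpoint in a SAP amended shortly before final database lock.

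**Conclusion.** The point holds for the primary Stage V percentage and age at Stage V. Both can be more favourable than breast/genital development, never less, and that direction follows from the definition alone. The size cannot be known from the documents: under the stated assumptions a 1-year breast/genital delay moves mean composite age by 0.24 to 0.32 year with equal component means, and by 0.02 to 0.76 year across a 1-year difference either way. The dilution shrinks if everolimus also delays pubic hair. The remaining outputs are partial safeguards. This is a cheap improvement to reporting, not a defect that invalidates the endpoint.

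**What to change.** In SAP 3.8.2 and 3.9.2:

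- Keep the either-component Stage V result as the pre-specified primary.
- Add supplementary rows for the percentage at stage 5 by 16/17 and for age at Stages II to V, separately for breast/genitalia and for pubic hair. Include age at genital stage 2 in boys. Do the same for TOSCA where components are recorded.
- List the breast/genital stage and age at exit for every patient who completed on pubic hair alone.
- Report the breast/genital percentage twice, with those patients counted as not reached and then as reached. Censoring them at exit may be informative, so a single Kaplan-Meier figure should not carry the result.

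**Cost.** A few extra tables and no new visits, since staging is defined by component (Protocol 7.2.2.2). Component-level data capture should be confirmed for both studies, as should the rule behind Stage V in TOSCA. The downside is an incomplete breast/genital outcome for patients who left on pubic hair alone; added tables cannot recover it.
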